5.4 Dose Limiting Toxicity

Dose-limiting toxicities are defined as the following toxicities if they occur anytime within the first 5 weeks of starting azacitidine (anytime within Cycle 1) and are thought to be secondary to azacitidine in combination with daratumumab:

- Grade 4 neutropenia lasting more than 7 days.
- Grade 4 thrombocytopenia lasting more than 7 days despite transfusion support.

- Grade 3 or higher non-hematological toxicity except:
 - Grade 3 nausea, vomiting or diarrhea that can be controlled within 48 hours with maximal supportive care.
 - Grade 3 hyperglycemia that can be controlled within 48 hours with appropriate supportive care.
 - Asymptomatic new Grade 3 or higher electrolyte disturbances that can be controlled with repletion or other medical management within 24 hours.

Severity of AEs will be graded according to CTCAE Version 5.0. As described in [Section 8.2.2](#), interim analysis will occur after accrual of 6 patients in the safety cohort. Study accrual will be stopped until these 6 patients have completed at minimum 5 weeks of treatment after starting azacitidine (ie completed Cycle 1), at which point a formal interim safety analysis will be performed with assessment for DLTs as defined above and safety stopping bounds for DLTs as described in [Section 8.2.2](#). Guidelines for dose reductions of azacitidine due to toxicity or dose delays/holding for daratumumab toxicity are detailed in [Section 5.5](#).

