7.7 Expedited Reporting

Reporting to the Data and Safety Monitoring Committee

If a death occurs during the treatment phase of the study or within 30 days after the last administration of the study drug(s) and it is determined to be related either to the study drug(s) or to a study procedure, the Investigator or his/her designee must notify the DSMC Chair (or qualified alternate) within 1 business day of knowledge of the event. The contact may be by phone or e-mail.

Reporting to Institutional Review Board

The UCSF PI must report events to the UCSF IRB according to institutional guidelines.

UCSF IRB website for guidance in reporting adverse events: <https://irb.ucsf.edu/adverse-event>

Expedited Reporting to the FDA

If the study is being conducted under an IND, the Sponsor (or the Sponsor-Investigator) is responsible for determining whether or not the suspected adverse reaction meets the criteria for expedited reporting in accordance with federal regulations (21 CFR §312.32).

The Sponsor (or Sponsor-Investigator) must report in an IND safety report any suspected adverse reaction that is both serious and unexpected. The Sponsor needs to ensure that the event meets all three definitions:

- Suspected adverse reaction
- Unexpected
- Serious

If the adverse event does not meet all three of the definitions, it should not be submitted as an expedited IND safety report.

The timeline for submitting an IND safety report to FDA is no later than **15 calendar days** after the Investigator determines that the suspected adverse reaction qualifies for reporting (21 CFR 312.32(c)(1)).

Any unexpected fatal or life-threatening suspected adverse reaction will be reported to FDA no later than **7 calendar days** after the Investigator's initial receipt of the information (21 CFR 312.32(c)(2)).

Any relevant additional information that pertains to a previously submitted IND safety report will be submitted to FDA as a Follow-up IND Safety Report without delay, as soon as the information is available (21 CFR 312.32(d)(2)).

Interventional IIS Janssen Scientific Affairs Requirements for Safety Data Collection and Reporting

Special Reporting Situations

Safety events of interest for a J&J medicinal product that require expediting reporting and/or safety evaluation include, but are not limited to:

- Drug exposure during pregnancy (maternal and paternal)
- Overdose of a J&J medicinal product
- Exposure to a J&J medicinal product from breastfeeding

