8.2 Analyses

Analyses Population

Analysis of primary and secondary efficacy variables will be based on the response-evaluable population, which includes all subjects who have measurable disease and received at least 2 cycles of study treatment, and have at least 2 efficacy evaluation assessments. All safety analyses for AEs will be based on the safety analysis set, which includes all subjects who receive at least 1 cycle of study treatment.

Safety Analysis

The study will begin with accrual of 6 patients in a safety run-in with interim safety analysis occurring after these 6 patients have completed at minimum Cycle 1 and further accrual stopped until safety analysis completed. If $\geq 2/6$ patients in the safety cohort have dose limiting toxicities (DLTs) as defined in [Section 5.4](#), then further study accrual will be halted until the study PI, co-investigators, and the DSMC can review the data, and determine whether the study should continue, be amended with a lower starting dose of azacitidine, or be closed to further accrual. Toxicities will be monitored throughout the study using CTCAE 5.0 criteria. Though we do not expect to observe DLTs during the study period, formal safety bounds based upon monitoring DLTs as defined in [Section 5.4](#) will guide decisions about early stopping due to potential safety concerns. A Pocock-type sequential boundary⁵⁹ will be used to monitor dose-limiting toxicities with the aim of keeping the probability of early stopping at around 90% if the true underlying toxicity rate is 25%. If the number of dose-limiting toxicities is equal to or exceeds the stopping boundaries detailed in the following table at any point in the study, then accrual to the study will be suspended until the study PI, co-investigators, and the DSMC can review the data, and determine whether the study should continue, be amended with a lower starting dose of azacitidine, or be closed to further accrual. With a toxicity rate of 25%, the expected number of enrolled patients before stopping for excessive toxicities is 6.5.

Table 8-1. Table: Safety monitoring bounds for DLTs

Number of subjects	Stopping boundary
6-9	≥ 2
10-14	≥ 3
15-18	≥ 4
19-23	≥ 5

Adverse Events

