8.3 Interim Analyses and Study Stopping Rules

As described in [Section 8.2.2](#), interim analysis will occur after accrual of 6 patients in the safety lead-in. Study accrual will be stopped until these 6 patients have completed at minimum cycle 1 of treatment, at which point a formal interim safety analysis will be performed with assessment for DLTs as defined in [Section 5.4](#) and safety stopping bounds for DLTs as described in [Section 8.2.2](#) and included again in the table below. If $\geq 2/6$ patients have DLTs, then further accrual to the study will be suspended until the study PI, co-investigators, and the DSMC can review the data, and determine whether the study should continue, be amended with a lower starting dose of azacitidine, or be closed for further accrual. Otherwise, study will continue. Safety monitoring will continue for the remaining duration of the trial. A Pocock-type sequential boundary⁵⁹ will be used to monitor dose-limiting toxicities with the aim of keeping the probability of early stopping at around 90% if the true underlying toxicity rate is 25%. The accrual will be halted until further study investigation if excessive numbers of dose-limiting toxicities are observed, that is, if the number of dose-limiting toxicities is equal to or exceeds the stopping boundaries in the following table. With a toxicity rate of 25%, the expected number of enrolled patients before stopping for excessive toxicities is 6.5.

Table: Safety monitoring bounds for DLTs

Number of subjects	Stopping boundary
6-9	≥ 2
10-14	≥ 3
15-18	≥ 4
19-23	≥ 5

As described previously in [Section 8.1](#), interim efficacy analysis will occur after completion of Simon's Stage I. 13 patients will be enrolled in Simon's Stage I. If there are 1 or fewer responses in these 13 patients, the study will be stopped. Otherwise, 10 additional patients will be accrued for a total of 23.

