3.2 Serious Adverse Event Reporting

By definition, an adverse event is defined as a serious adverse event (SAE) according to the following criteria:

- Death.
- Life-threatening (i.e., results in an immediate risk of death).
- Requires inpatient hospitalization or prolongation of existing hospitalization,
- Permanent or significant disability/incapacity
- Gives rise to a congenital anomaly/birth defect, or cancer, or any experience that suggests a significant hazard, contraindication, side effect, or precaution that may require medical or surgical intervention to prevent one of the outcomes listed above.
- Event occurring in a gene therapy study.
- Event that changes the risk/benefit ratio of a study.
- Any other event the Principal Investigator judges to be serious or which would suggest a significant hazard, contraindication, side effect, or precaution.

Serious adverse event reporting will be in accordance with all IRB regulations. For trials conducted under an investigational new drug (IND) application, the SAE will be reported in accordance with Code of Federal Regulation Title 21 Part 312.32 and will be reported on a Med Watch form.

UCSF IRB website for guidance in reporting serious adverse events:
<https://irb.ucsf.edu/adverse-event>

Med Watch forms and information:
www.fda.gov/medwatch/getforms.htm

All serious adverse events are entered into OnCore®, as well as submitted to the IRB (per IRB guidelines). The SAEs are reviewed and monitored by the Data and Safety Monitoring Committee on an ongoing basis and discussed at DSMC meetings, which take place every six weeks. The date the SAE is sent to all required reporting agencies will be documented in OnCore®.

If the SAE involves a subject death, and is determined to be possibly, probably or definitely related to the investigational drug or any research related procedure, the event must be reported to the DSMC Chair (or Vice Chair) and DSMC Director within one business day.

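### In the visible text, a treatment-related death does not by itself suspend accrual; whether to pause is left to discretion

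*Combined protocol and SAP*

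**What the plan says.** Section 8.2 (Safety Analysis) and Section 8.3 contain two toxicity rules that suspend accrual. The first applies when at least 2 of the 6 lead-in patients have DLTs. The second applies throughout: "If the number of dose-limiting toxicities is equal to or exceeds the stopping boundaries detailed in the following table", with limits of 2 (6-9 subjects), 3 (10-14), 4 (15-18) and 5 (19-23). Either rule sends the data to the PI, co-investigators and DSMC, who decide whether the study continues, is amended or closes.

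Both rules use the Section 5.4 definition. The listed toxicities are DLTs "if they occur anytime within the first 5 weeks of starting azacitidine (anytime within Cycle 1" and only if attributed to azacitidine in combination with daratumumab. Death is not a listed item; a fatal non-hematological event in Cycle 1 qualifies as Grade 3 or higher.

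Accrual is also held once after patient 6, whatever the count ("Study accrual will be stopped until these 6 patients have completed at minimum 5 weeks of treatment after starting azacitidine"). If fewer than 2 of the 6 have DLTs, Section 8.3 says "Otherwise, study will continue".

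Related deaths are otherwise handled by reporting. Under Section 7.7 the investigator "must notify the DSMC Chair (or qualified alternate) within 1 business day of knowledge of the event", and Appendix 2 Section 3.2 sets the same time limit. Appendix 2 also provides for continuing DSMC review of serious adverse events, which are "discussed at DSMC meetings, which take place every six weeks", and for monthly site committee review of all Grade 3-5 events.

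**The concern.** This is the first study of the combination, and Section 1.3 names toxicity, particularly cytopenias and infections, as its main risk. Section 3.1 anticipates about 8 months of participation, so most exposure falls after the five-week DLT window. A death attributed to treatment is the clearest safety signal a study of this size can produce. Yet neither counting rule responds to one such death, and neither counts late deaths at all. A team following the plan to the letter could start new patients on the same regimen while the death is still under review.

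**Working it through.** **1. What the plan states for Table 8-1.** The plan gives about 90% probability of stopping and 6.5 patients expected at a 25% DLT rate. An exact binomial recursion, checking the limits after each patient from the 6th, gives 85.5% and 10.4 patients (8.3 among trials that stop). That mismatch is a separate matter. The present point does not depend on it.

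**2. What one related death adds to the counts.**

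| Timing of death | DLTs added | Lowest limit | Suspends by itself? |
|---|---|---|---|
| After Cycle 1 | 0 | 2 | No |
| Cycle 1, non-hematological | at most 1 | 2 | No |

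The table limit may be checked at any point in the study, but that fixes when the count is compared and does not widen the Section 5.4 window. Any number of deaths after Cycle 1 still adds 0. A Cycle 1 death suspends accrual only if the count already stood one below the limit. At 1 DLT in 6 patients the study continues, even if that DLT was fatal.

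**3. Patients who could start before a scheduled meeting.** Section 8.4 expects 2-3 patients per month. Six weeks is 6/4.35 = 1.38 months, so uninterrupted accrual would give 2 × 1.38 = 2.8 to 3 × 1.38 = 4.1 patients. Planned halts lower this. A simulation used a 5-week halt after patient 6, a 9-week halt after patient 13 (Cycle 1 plus Cycle 2), and death times uniform from week 5 to either 8 months (anticipated treatment) or 3.5 months (median PFS quoted in Section 1.3).

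- Full six-week wait: mean 1.8 to 2.9 patients.
- Death at a random point between meetings (mean wait 3 weeks): about 1.0 to 1.4.
- Section 3.1 instead estimates accrual over 12-18 months, that is 23/18 = 1.3 to 23/12 = 1.9 per month. The full six-week figure is then about 1.5 to 2.0.

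**4. How often the gap could matter.** The documents give no related-death rate for the combination. In Table 1-1, none of the fatal events among 156 daratumumab monotherapy patients was considered related (one-sided 95% upper limit 1 − 0.05^(1/156) = 1.9%). In the azacitidine safety text of Section 1.2, no deaths were attributed to azacitidine. Rates q of 1% and 2% after Cycle 1 are therefore assumed. With F_i the share of patient i's death-time range that precedes the last enrolment, P = 1 − ∏(1 − qF_i). At 2-3 per month with all 23 enrolled, the chance of at least one late related death while accrual is open is 11-16% (q = 1%) or 21-30% (q = 2%). At the Section 3.1 accrual it is 14-18% or 26-33%. If the true response rate is 8%, the Stage 1 futility stop has probability 0.92^13 + 13 × 0.08 × 0.92^12 = 0.72, and at 2-3 per month the chances fall to 5-10% and 10-19%.

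**5. How often a one-death rule would pause accrual.** The formula is the same, with death times uniform from the first dose and all 23 enrolled at 2-3 per month.

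| Assumed related-death rate | Trials with at least one pause |
|---|---|
| 1% | 12-17% |
| 2% | 23-32% |
| 5% | 49-62% |

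The 5% row is a stress case. Table 1-1 reports deaths from treatment-emergent events of 21/318 (6.6%) with lenalidomide-dexamethasone and 13/243 (5.3%) with bortezomib-dexamethasone. Relatedness is not given for these.

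**The case against.** The strongest reply is that the plan already has a working, discretionary system. The DSMC Chair hears of a related death within one business day. Appendix 2 has serious events reviewed continuously as well as at scheduled meetings, and the site committee meets monthly. If the study is under an IND, Section 7.7 requires a report to FDA within 7 days for an unexpected fatal suspected reaction. Section 9.4 allows an immediate-hazard amendment before IRB approval. Automatic or discretionary pausing is a legitimate design choice.

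Most of this stands, and it limits what can be claimed. A reader might infer that a related death would go unreviewed for six weeks. The documents do not support that: six weeks is the spacing of meetings, so it is the longest wait for a scheduled one and not the expected review delay. A reader might also infer that the DSMC could not halt the study after one death. Nothing in the text says so.

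What the reply does not supply is a sentence that holds enrolment while the review takes place. Reporting and review duties leave the next patient free to start.

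The objection that a broad trigger costs more than low death rates suggest also stands. Deaths called possibly related could be commoner than 1-2%, and the 5% row shows the effect.

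**Conclusion.** The point holds as a gap in the visible rules that is cheap to close. The count argument needs no assumed rate: 0 or at most 1 DLT against a lowest limit of 2. The exposure figures do rest on assumptions: the accrual rate, the length of the halts, the spread of death times, and nobody acting before a scheduled meeting.

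A reader might go further and conclude that the plan as a whole has no such rule. That cannot be said, because a page directly after the serious-adverse-event text of Appendix 2 is missing from the copy available. Sections 5.4, 7.7, 8.2, 8.3 and 9.7, where such a rule would be expected, are visible and contain none.

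**What to change.** Add one sentence to Sections 8.2 and 8.3. Any death judged possibly, probably or definitely related to a study drug or study procedure, during treatment or within 30 days after the last dose (or later if judged related), suspends new enrolment. The suspension lasts until the PI, co-investigators and the DSMC, convened ad hoc and not held over to the scheduled meeting, have reviewed the death and decided whether the study continues, is amended or closes.

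The change is to wording only, because the one-business-day report, the review group and the decision options already exist. The downside is the occasional pause sized above. The ad hoc review is meant to keep each pause short, although the sentence sets no time limit. Patients already on treatment are not affected by the enrolment hold itself.

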8.1 Sample Size Determination

This is a single-arm, open-label, 2-stage phase II study designed to evaluate the efficacy of daratumumab in combination with azacitidine and dexamethasone in RRMM patients previously treated with daratumumab. A Simon's two-stage design⁵⁸ will be used for this study. The study will begin with accrual of 6 patients in a safety run-in. Safety monitoring bounds for study termination based on DLTs are described in [Section 8.2.2](#). If the safety stopping bounds are not met, study will continue to accrue more Stage I patients.

Sample size calculation was based on assessing the overall response rate (ORR) using Simon's minimax 2-stage design. Interim analysis for efficacy, using ORR, will be performed when the last patient enrolled to Stage 1 has received at least 2 cycles of treatment.

The overall target sample size of 23 patients is based upon having sufficient information to assess whether combined treatment of daratumumab with azacitidine and dexamethasone increases the ORR in this study population of RRMM patients with prior treatment with daratumumab. Data from ongoing clinical trial evaluating the safety, pharmacokinetics, and efficacy of isatuximab in patients with RRMM previously treated with daratumumab has shown preliminary results of ORR 8% (NCT02514668). Isatuximab is another CD38 monoclonal antibody with similar efficacy to daratumumab in RRMM patients.²⁴ Based on these previous results, for this study we would be interested in detecting an improvement in the ORR from a null rate of 8% to 33% ORR, which is based on the daratumumab-pomalidomide-dexamethasone

combination study in patients with RRMM re-treated with daratumumab.²³ Simon's minimax two-stage design will be used. The null hypothesis that the true response rate is 8% will be tested against a one-sided alternative that the true response rate is higher than 33%. In the first stage, 13 patients will be accrued. If there are 1 or fewer responses in these 13 patients, the study will be stopped. Otherwise, 10 additional patients will be accrued for a total of 23. The null hypothesis will be rejected if 5 or more responses are observed in 23 patients. The design will have a 90% power to reject the null hypothesis, if the true response rate is 33%, at one-sided 5% significance level. Accounting for an approximate 10% drop-out/ineligibility rate, maximum target accrual should not exceed 25 participants.

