8.4 Accrual Estimates

There are around 1500 active myeloma patients being seen at UCSF. We would expect to accrue about 2-3 patients per month, which ideally would mean 8-12 months for patient accrual.

9 Study Management

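### The stated expected enrolment of 6.5 patients at a 25% DLT rate does not follow from the printed stopping table, which gives about 10.4 overall, or 8.3 among trials that stop

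*Combined protocol and SAP*

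**What the plan says.** Section 8.2 (Safety Analysis) describes the monitoring as follows: "A Pocock-type sequential boundary⁵⁹ will be used to monitor dose-limiting toxicities". The design goal given there is that about 90% of trials should stop early when the DLT rate is 25%. Table 8-1 sets the bounds: 2 or more DLTs at 6-9 patients, 3 or more at 10-14, 4 or more at 15-18, and 5 or more at 19-23. There is no row below 6, and the first formal look comes once the six lead-in patients have completed Cycle 1. The bounds then apply at any point in the study. Reaching one suspends accrual for review by the investigators and the DSMC; it does not close the study automatically.

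The performance claim is: "With a toxicity rate of 25%, the expected number of enrolled patients before stopping for excessive toxicities is 6.5". Section 8.3 repeats the table and the claim ("the expected number of enrolled patients before stopping for excessive toxicities is 6.5"). Neither section says whether 6.5 is averaged over all trials or only over trials that stop, or how a trial that never stops is counted.

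**The concern.** With the first look at 6 patients, a mean of 6.5 implies that nearly every trial stops at that look or very soon after. A bound of 2 DLTs in 6 patients does not do this at a 25% rate: fewer than half of trials reach it.

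Section 1.3 names toxicity as the main risk of a combination that has had no prior trial. A DSMC or IRB member asking how many patients would be exposed before the rule acts at 25% has only this number to go on. It suggests suspension at, or one patient after, the lead-in. If the true mean is materially higher, the protection is overstated.

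**Working it through.** **Inputs.** The DLT rate p = 0.25 and the bounds come from Section 8.2, and the maximum of 23 patients from Section 8.1. Looks are taken after each patient from 6 to 23. Each outcome is assumed known before the next enrolment.

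**Can 6.5 be an overall mean at all?** No trial stops before patient 6. If a proportion s ever stops, overall E[N] is at least 6s + 23(1 − s). At the stated aim of s = 0.90 this is 0.9 × 6 + 0.1 × 23 = 7.7, even with every stop falling exactly at 6. An overall mean of 6.5 would need s of at least (23 − 6.5)/17 = 0.97. So the plan's own 90%, first look at 6 and total of 23 already rule it out. This bound does not rule out 6.5 as a mean among stopped trials; that needs the full calculation.

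**First steps by hand.**

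- P(stop at 6) = 1 − 0.75⁶ − 6(0.25)(0.75⁵) = 1 − 0.1780 − 0.3560 = 0.466, so 53.4% pass the lead-in check.
- P(stopped by 7) = 1 − 0.75⁷ − 7(0.25)(0.75⁶) = 0.555.
- P(stopped by 9) = 1 − 0.75⁹ − 9(0.25)(0.75⁸) = 0.700, so 30.0% are still open after patient 9.

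**Full table.** This is a binomial recursion on the DLT count, removing trials when they reach the bound. Probability of first reaching the bound at patient n:

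| n | P | n | P | n | P |
|---|---|---|---|---|---|
| 6 | 0.4661 | 12 | 0.0223 | 18 | 0.0145 |
| 7 | 0.0890 | 13 | 0.0264 | 20 | 0.0040 |
| 8 | 0.0779 | 14 | 0.0277 | 21 | 0.0072 |
| 9 | 0.0667 | 16 | 0.0068 | 22 | 0.0095 |
| 11 | 0.0141 | 17 | 0.0115 | 23 | 0.0110 |

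No trial can stop at 10, 15 or 19, because the bound has just risen by one.

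- P(stop) = sum of P = 0.855.
- Sum of n × P = 7.06.
- E[N] overall = 7.06 + 23 × 0.1453 = 10.40.
- E[N given stop] = 7.06 / 0.8547 = 8.26.
- Median stopping point: patient 7.

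A simulation of 400,000 trials agrees (85.5%, 10.41, 8.26).

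**Other readings, all at 25%.**

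| Reading | E[N] overall | E[N given DLT stop] |
|---|---|---|
| Printed table, patients 6-23 | 10.4 | 8.3 |
| Last bound carried to 25 patients | 10.7 | 8.7 |
| Bound of 2 also applied from patient 2 | 9.6 | 7.3 |
| With Simon futility stop at 13, ORR 8% | 9.0 | 7.4 |
| With Simon futility stop at 13, ORR 33% | 10.3 | 8.2 |
| With assessment lag, 2-3 patients per month | 11.2-11.7 | 9.2-9.7 |

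The 25-patient row uses the ceiling in Section 8.1 ("maximum target accrual should not exceed 25 participants"). The lag row uses the pause in Section 5.4 ("Study accrual will be stopped until these 6 patients have completed at minimum 5 weeks of treatment after starting azacitidine") and the rate in Section 8.4 ("We would expect to accrue about 2-3 patients per month"). It also assumes random arrivals and a pause only at 6, neither of which the plan specifies. No row gives 6.5.

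**Inversion.** On the printed table, overall E[N] equals 6.5 at a DLT rate of 0.457, and E[N given stop] equals 6.5 at 0.451.

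**The case against.** The strongest reply is that little turns on the number. No sample size, analysis or decision uses 6.5. The bounds are explicit and identical in both sections, and reaching one leads to a review, not automatic closure. The median stopping point is patient 7, so the impression of suspension around the lead-in is fair for a typical trial; the mean is higher because of late stops and trials that never stop. All of this stands and limits the weight of the point. It does not make 6.5 correct, because the plan calls it an expected number.

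A second reply is that 6.5 is the mean among stopped trials, with bounds active before patient 6. Applying the bound of 2 from patient 2 narrows the conditional gap from 27% to about 12% (7.26 / 6.5 = 1.12). It still misses, and the table has no row below 6.

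A third is that the stopping probability is only an aim of around 90%, and reaches 87.9% if the last bound runs to 25 patients. That is fair: 85.5% is a missed aim, not a false statement.

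There is also a possible explanation. A boundary that matches the printed rows from 6 onward, but also stops on 1 DLT among the first 3 or 4 patients and on 2 after that, gives E[N] of 6.83 or 6.27 and stopping probabilities of 88.6% or 89.6%. These bracket 6.5 and fit around 90%. The documents do not say this, so it remains inference. It does suggest that both stated figures may describe a boundary other than the one printed.

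**Conclusion.** The concern holds. The stated 6.5 is not a property of the printed table on either reading. Overall expected enrolment is 10.4, or 60% above the stated figure (10.4 / 6.5 = 1.60). Among trials that stop it is 8.3, or 27% above (8.26 / 6.5 = 1.27). These results assume a 25% DLT rate, independent patients, a look after each patient from 6 to 23, outcomes known before the next enrolment, and no futility stop. The variants change the figures but none reaches 6.5. The error lies in the stated performance of the safety rule, not in the rule or in how any patient is handled. It should be corrected because it is the only figure given for how soon the rule acts at the rate it was designed around.

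**What to change.** Regenerate the table, the stopping probability and the expected number from one calculation, so that all three describe the same boundary. This comes first because the present figures may belong to a different boundary, and restating them alone could hide that. The choice of boundary is the sponsor's; the table and the sentences about it must be reconciled in Sections 8.2 and 8.3 alike.

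If the printed table is the intended one, replace the 6.5 sentence in both sections with wording to this effect: *At a DLT rate of 25%, with monitoring after each patient from 6 to 23, the boundary is reached with probability about 85%. Expected enrolment is about 10.4, counting trials that do not reach it as 23, and about 8.3 among trials that do. These figures assume that each DLT outcome is known before the next enrolment and ignore the efficacy futility stop.*

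Restating costs one or two sentences in each of two sections, with no change to the rule, the sample size or conduct. The stated performance becomes less favourable. If the table itself turns out not to be the intended one, correcting it changes the monitoring rule and needs an amendment.
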